#### 13 STATISTICAL METHODS AND DETERMINATION OF SAMPLE SIZE

#### 13.1 Statistical and Analytical Plans

Before the unblinding of the study data, a separate statistical analysis plan (SAP), which will provide the technical details of the statistical analysis outlined below, will be prepared and approved.

## 13.1.1 Data Sets to be Analysed

The participant population sets are defined as follows:

**Full analysis set (FAS):** All participants who are diagnosed with a history of AD and who are randomised for the treatment.

**Per-protocol set (PPS):** All participants who are deemed to have no major protocol violations that could interfere with the objectives of this study. This is a sub-population of the FAS.

Note: Important violations of eligibility criteria and other deviations from the protocol will be assessed in cooperation with the Sponsor. Important deviations from the protocol may lead to exclusion of a participant from the PPS. All deviations will be discussed and agreed prior to the unblinding of the data.

**Safety set:** All randomised participants who receive at least 1 dose of test or reference cream.

Although the primary analysis will be performed on both the FAS and the PPS, the FAS will be considered the primary analysis population. Secondary analyses will be performed on the FAS only.

Safety summaries will be performed on the safety set.

#### 13.1.2 Statistical Issues

#### Handling of Drop-outs or Missing Data

Missing data will not be replaced. The drop out rate will be calculated and analysed. Further details will be presented in the SAP.

#### **Blind Review**

Prior to code breaking, a blind review of the data will be performed. The objective of the review is to identify problems and to make decisions regarding data analytical issues under blind conditions.

## 13.1.3 Summary Statistics

Data will be summarised using appropriate descriptive statistics such as mean and standard deviation, minimum and maximum. If appropriate, median and quartiles may be presented in place of the mean and standard deviation. Further details will be given in the statistical analysis plan.

Demographic and patient history data collected at screening and baseline visits will be summarised.

Confidential Page 53 of 65

Version: Version 3.0 Date: 15 August 2019 Sponsor: ACO Hud Nordic AB Study Code: Novum ACO-CT-2018-01 EudraCT No.: 2018-002945-12

## 13.1.4 Primary Efficacy Analysis

The primary analysis will compare the test treatment to no treatment and to the two reference creams in terms of change in TEWL and redness between days 31 and 29.

The statistical analysis technique used must take account of the design of the study, such that each participant has four 'matched' treatment areas. In addition, the choice of analysis must consider the distribution of the data, as it is likely that both TEWL and redness score will be skewed. Therefore, both transformations combined with parametric tests and non-parametric tests which take account of the 'matched' nature of the data will be considered. Where possible and appropriate the baseline values will be included as a covariate. Further details will be outlined in the SAP.

These analyses will be carried out on the FAS and PPS.

## 13.1.5 Secondary Efficacy Analyses

The secondary analyses will compare the test treatment to no treatment and to the two reference treatments in terms of change in TEWL and skin moisturisation as measured by capacitance and skin surface dryness from baseline to day 29.

The analyses of these outcomes will follow the same plan as the primary analyses.

Skin moisturisation as measured by NMF levels will not be recorded at baseline and therefore the analysis will compare the treatments in terms of the data observed at day 29 using a suitable analysis, taking account of the distribution of the data and the 'matched' nature of the observations.

Patient tolerability scores will not be recorded prior to treatment and so will be summarised by timepoint (day 1, day 5 and day 29) and the treatments compared using a suitable analysis, taking account of the distribution of the data and the 'paired' nature of the observations.

Tolerability properties as measured by investigator visual scores for redness and objective erythema from 2D colour skin images: The change from baseline to day 15 and from baseline to day 31 will be compared between treatments using a suitable analysis, in a similar way to the primary analyses.

The secondary analyses will be carried out on the FAS.

## 13.1.6 Other Analyses

The total consumption of the creams (test or reference cream), based on cream weight, will be calculated and tabulated descriptively. If appropriate consideration will be given to including the cream consumption as a covariate in the model or in an exploratory analysis of the primary endpoints.

The number of FLG loss-of-function mutation carriers will be summarised. If sufficient participants with the mutation are detected then descriptive tabulations of TEWL by mutation status will be presented.

#### 13.1.7 Demographic and Other Baseline Characteristics

Participant disposition, demographic and other baseline data will be presented using summary statistics. Both the FAS will be used for this presentation.

Confidential Page 54 of 65

Version: Version 3.0 Date: 15 August 2019

## 13.1.8 Exposure to Treatment and Treatment Compliance

For exposure to treatment, the total consumption of the test and reference creams will be calculated. The FAS set will be used for this presentation.

For treatment compliance, data from the participant diaries will be used.

#### 13.1.9 Adverse Events

AEs will be coded using the Medical Dictionary for Regulatory Activities and tabulated by system organ class and by preferred term.

Sponsor: ACO Hud Nordic AB

EudraCT No.: 2018-002945-12

Study Code: Novum ACO-CT-2018-01

The total number of participants with at least 1 AE and the total number of AEs will be presented.

The number of participants and the number of AEs will be tabulated by system organ class and by preferred term. AEs will also be tabulated versus worst severity and worst relationship to treatment. Finally, for those AEs which are specifically recorded as related to one of the test sites the AEs will be summarised by test site. A listing, by participant number, will also be produced which lists the AEs with worst severity and worst relationship to treatment.

## 13.2 Determination of Sample Size

The sample size for this study is based on the primary end point, change in TEWL after induction of skin irritation (change between day 19 and day 21), with the primary comparison being between the test treatment and no treatment and the secondary comparison being between the test treatment and the two reference treatments.

In a similar study the standard deviation of the difference in change in TEWL after induction of skin irritation was seen to be approximately 8 g/m²/h when comparing the no treatment group to an active treatment. (that is: standard deviation of {[Change after skin irritation in no treatment area]-[Change after skin irritation in active treatment area]}).

When comparing the difference between the test treatment and one of the two reference treatments the standard deviation was approximately 3.

If the assumptions of a paired t-test are found to be valid, for a sample of 40 participants this analysis would have >90% power to detect a difference (in change) of 3.5 g/mÇ.h between test treatment and no treatment. The same sample size would also have >90% power to detect a difference (in change) of 2 g/mÇ.h between test treatment and active treatment. If a parametric analysis is indicated then an analysis which includes the baseline as a covariate will be considered which, if there is variation at baseline may increase the power of the analysis further.

If the assumptions of a paired t-test are not met (and a suitable transformation cannot be found) then a sign test (or a wilcoxon matched pairs test) may be used. A power calculation can be carried out for the sign test (46) although this too makes some assumptions. This calculation shows that a sample size of N=40 would have >80% power to detect a difference such that the probability of X>0 (where X is the difference in change, as above) is approximately 0.7. This probability is not unrealistic given the data seen previously, and, if the clinically relevant difference detailed above is seen, the probability of X>0 may in fact be increased leading to higher power. To account for dropouts, 50 subjects will be recruited.

Confidential Page 55 of 65

Version: Version 3.0 Date: 15 August 2019 Sponsor: ACO Hud Nordic AB Study Code: Novum ACO-CT-2018-01 EudraCT No.: 2018-002945-12

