#### NUMBER OF PARTICIPANTS and statistical evaluation:

50 participants will be recruited into the study. This sample size is sufficient to provide more than 90% power to detect a difference (test treatment vs no treatment) of 3.5 in change in TEWL for the primary endpoint, if the data is suitable for a parametric analysis. If the observed data is not suitable for a parametric analysis then the sample size would provide greater than 80% power in a non parametric analysis.

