#### 9 SELECTION OF STUDY POPULATION

#### 9.1 Number of Participants

It is estimated that 50 evaluable participants will be needed (see Section 13.2 for sample size calculation).

Sponsor: ACO Hud Nordic AB

EudraCT No.: 2018-002945-12

Study Code: Novum ACO-CT-2018-01

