# 2. Study Methods

# 2.1 Study Design

It is planned to recruit 40 adults (male and female, aged 18 and above) with personal history of atopic dermatitis but no current eczema on the volar forearms and no possible allergy to the ingredients in the study medications.

Four treatment sites on the lower volar forearms (two on the right and two on the left) will be randomised for each participant with one treatment to be applied to each of three sites and the fourth remaining untreated as a control. The four treatment groups are;

- No treatment (control)
- Miniderm Novum (test cream)
- Miniderm 20% (reference cream)
- Diprobase (reference cream)

One Finger Tip Unit (FTU) of each cream will be applied twice daily on the designated study area. The participants will record details of cream application frequency, as well as participant tolerability in a diary.

Subjects will remain in the study for 4-5 weeks.

At each study visit, concomitant medication and any AEs are noted in the Case Report Form (CRF). The study medication will be collected and weighed in order to estimate cream consumption.

Participants will attend 5 clinic visits during the study:

- Visit 1 (screening) will be performed at baseline (Day 1)
- Visit 2 will be performed after 5 days of treatment
- Visit 3 will be performed after 15 days of treatment

- Visit 4 will be performed after 29 days of treatment
- Visit 5 will be performed 1 day after SLS-patch removal (Day 31)

Assessors will be blind to the treatment assigned to each site. Subjects will be blinded to the cream assigned to each study site – although the untreated site will remain unblinded.

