# 7.5 Multiplicity considerations

All analyses in this SAP will be carried out with a two sided 5% significance level.

Secondary analyses are considered to be exploratory and so no adjustment will be made for multiplicity.

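### The stated >90% power for test cream versus no treatment is wrong: the plan's own inputs give 77% with 40 participants and 86% with 50, and the >80% sign-test figure at N=40 holds only one-sided

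*Protocol*

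**What the plan says.** Protocol 13.2 sizes the trial on the change in TEWL after skin irritation, and names test cream versus no treatment as the primary comparison. The SD of the paired difference "was seen to be approximately 8 g/m²/h when comparing the no treatment group to an active treatment". The text defines this as the "standard deviation of {[Change after skin irritation in no treatment area]-[Change after skin irritation in active treatment area" quantity, so it is already the SD of a within-participant difference in change.

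From these inputs the protocol claims, for a paired t-test, that "for a sample of 40 participants this analysis would have >90% power to detect a difference (in change) of 3.5" g/m²/h. If the t-test assumptions fail and no transformation helps, it claims for the sign test that "a sample size of N=40 would have >80% power to detect a difference such that the probability of X>0" is about 0.7. SAP 2.3 repeats both statements. The synopsis attaches the parametric claim, for the TEWL endpoint, to 50 participants: "This sample size is sufficient to provide more than 90% power to detect a difference (test treatment vs no treatment) of 3.5 in change". It also claims more than 80% for a non-parametric analysis at that size.

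Protocol 13.2 gives no significance level. The only one in the documents is in SAP 7.5: "All analyses in this SAP will be carried out with a two sided 5% significance level".

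Three participant numbers appear. Protocol 13.2 recruits 50 to allow for dropouts from 40. SAP 2.1 says "It is planned to recruit 40 adults". Protocol 9.1 says "It is estimated that 50 evaluable participants will be needed" and cites 13.2 as its source.

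**The concern.** A standardised difference of 3.5/8 = 0.4375 in 40 pairs is too small for 90% power in a two-sided 5% paired t-test. The claim can be checked without outside information, because the SD, its definition, the difference, the test and the sample size are all in the plan.

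The affected comparison is the one the plan calls primary. If power is 77%, the risk of missing a true 3.5 g/m²/h effect is 23%, more than double the under-10% risk that the plan implies. A non-significant result would then be read as stronger evidence against an effect than the design allows.

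The fallback also matters. Protocol 13.1.4 expects TEWL and redness to be skewed, and SAP 7.1 keeps the Wilcoxon and sign tests as alternatives. Missing data are not replaced, so each dropout lowers the effective number. Recruiting 40, as SAP 2.1 says, would leave no allowance for dropouts.

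**Working it through.** **Inputs.** SD of the paired difference: 8 against no treatment and 3 against a reference cream (Protocol 13.2, SAP 2.3). Differences: 3.5 and 2 (same places). n = 40 (Protocol 13.2, SAP 2.3) or 50 (synopsis). Alpha: 0.05 two-sided (SAP 7.5). Sign test: P(X>0) = 0.7.

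**Paired t-test.** Power = P(|T| > t(1−α/2, n−1)), where T is noncentral t with n−1 degrees of freedom and noncentrality (difference/SD)·√n.

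The plan's claim against the reference creams reproduces. At n = 40 the noncentrality is (2/3)·√40 = 4.22 and power is 98.4%, in line with the stated >90%. The method therefore fits how the plan is written.

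For test cream versus no treatment, the noncentrality is 0.4375·√40 = 2.77 at n = 40 and 0.4375·√50 = 3.09 at n = 50.

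| n | SD | Two-sided 5% | One-sided 5% | Plan |
|---|---|---|---|---|
| 40 | 8 | 77.0% | 85.9% | >90% |
| 50 | 8 | 85.8% | 92.0% | >90% |
| 40 | 7.5 to 8.5 | 82% to 72% | – | >90% |
| 50 | 7.5 to 8.5 | 90% (89.9%) to 81% | – | >90% |

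The last two rows read the word 'approximately' in the plan as half a unit either way.

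What two-sided 90% power would need:
- 57 evaluable participants at 3.5/8; or
- a difference of about 4.2 at n = 40 or 3.75 at n = 50, with SD 8; or
- an SD of at most about 6.65 at n = 40 or 7.48 at n = 50, with difference 3.5.

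**Sign test.** Noether's formula, which the plan cites, is N = (z_α + z_β)² / [4(p − 0.5)²]. With p = 0.7 the denominator is 4 × 0.04 = 0.16.
- For 80% power, N = 49.1 two-sided and 38.6 one-sided. The plan's N=40 matches only the one-sided result.
- Inverting at N = 40, power = Φ(√(40 × 0.16) − z_α). This is Φ(2.530 − 1.960) = 71.6% two-sided and Φ(2.530 − 1.645) = 81.2% one-sided.
- The exact binomial test at N = 40, two-sided, rejects at 27 or more of 40 in the favourable direction (tail probability 0.019 under p = 0.5). Its power at p = 0.7 is 70.3%.
- At N = 50, two-sided: 80.7% by Noether and 78.2% exact.

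The plan suggests that a true difference of 3.5 could raise P(X>0) above 0.7. As a reference point only, normal differences with mean 3.5 and SD 8 give P(X>0) = Φ(0.4375) = 0.669. Two-sided Noether power is then 57% at N = 40 and 67% at N = 50.

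**The case against.** The arithmetic at n = 40 is not open to dispute, but several limits on the criticism are fair.

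**Sidedness.** Protocol 13.2 states neither alpha nor sidedness, and the hypotheses are directional. At one-sided 5%, the synopsis figure at 50 (92.0%) and the sign-test figure at 40 (81.2%) both hold. This explains how those two numbers may have arisen. It does not make them right for the planned analysis, because SAP 7.5 sets two-sided tests throughout. The N=40 t-test claim fails on either reading.

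**Synopsis figures.** The non-parametric claim at 50 is just met two-sided by Noether's formula (80.7%), though not by the exact test (78.2%), and only if nobody drops out. The sign-test criticism is therefore confined to N=40. With an SD of 7.5, the parametric claim at 50 comes within a fraction of a point of 90%, but the plan treats the extra ten participants as dropout cover.

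**Baseline adjustment.** SAP 7.1 specifies ANCOVA with the Day 29 value as covariate, which may have more power than the paired t-test. The plan presents that as a possible further gain, so it is not part of the >90%, and no correlation is given. Reaching 90% would need a variance reduction of about 1 − (6.65/8)² = 31% at 40, or 1 − (7.48/8)² = 13% at 50. The restated figures should still be labelled as unadjusted.

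**Normal-theory sign-test figures.** The 57% and 67% assume normal differences, in which case the t-test would be used. They only show that the plan's remark about P(X>0) is not assured; the conclusion does not rest on them.

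**Consequence.** The estimate and its confidence interval will not depend on the planning power, and nothing in the conduct changes. That limits the harm but does not make the stated figure correct.

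**Conclusion.** The concern holds. For test cream versus no treatment, the plan's inputs give 77.0% power at 40 and 85.8% at 50, against a stated >90% in each case. The shortfall is at least 13 points at 40 and 4 points at 50. The >80% sign-test figure at N=40 is a one-sided result; under the SAP's two-sided rule it is 71.6% (exact 70.3%). The claim for the reference creams is sound (98.4%).

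These figures rest on an SD of 8, a difference of 3.5, two-sided 5%, no covariate adjustment, and 40 or 50 evaluable participants as stated. At n = 40, no SD from 7.5 to 8.5 rescues the two-sided claim. The participant numbers in SAP 2.1 and Protocol 9.1 also conflict with Protocol 13.2, and the power statement depends on which applies. The power statement must be corrected because it is false on the plan's own numbers.

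**What to change.** Keep recruitment at 50 and change the text as follows.

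- **Synopsis, Protocol 13.2 and SAP 2.3, t-test:** state about 77% power for 3.5 g/m²/h with 40 evaluable participants, and about 86% if all 50 are evaluable. Give the differences detectable with 90% power, about 4.2 and 3.75 respectively. Say that these are unadjusted paired t-test figures at two-sided 5% with SD 8.
- **Sign test:** state about 70 to 72% at N=40, two-sided, for P(X>0) = 0.7. If the synopsis keeps its non-parametric figure, say that about 80% requires all 50 to be evaluable (80.7% by Noether, 78.2% exact).
- **Participant numbers:** correct SAP 2.1 to 50 recruited, and Protocol 9.1 to 40 evaluable of 50 recruited. Both then agree with Protocol 13.2, which 9.1 cites.

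The cost is wording only: no extra participants and no change to analysis or conduct. The sponsor has to accept a less favourable power statement.

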# 2.3 Sample size:

The sample size for this study is based on the primary end point, change in Trans Epidermal Water Loss (TEWL) after induction of skin irritation (change from day 29 to day 31), with the primary comparison being between the test treatment and no treatment and the secondary comparison being between the test treatment and the two reference treatments.

In a similar study the standard deviation of the difference in change in TEWL after induction of skin irritation was seen to be approximately 8 g/mÇ.h when comparing the no treatment group to an active treatment. (that is: standard deviation of {[Change after skin irritation in no treatment area]-[Change after skin irritation in active treatment area]}).

When comparing the difference between the test treatment and one of the two reference treatments the standard deviation was approximately 3.

If the assumptions of a paired t-test are found to be valid, for a sample of 40 participants this analysis would have >90% power to detect a difference (in change) of 3.5 g/mÇ.h between test treatment and no treatment. The same sample size would also have >90% power to detect a difference (in change) of 2 g/mÇ.h between test treatment and active treatment. If a parametric analysis is indicated then an analysis which includes the baseline as a covariate will be considered which, if there is variation at baseline may increase the power of the analysis further.

If the assumptions of a paired t-test are not met (and a suitable transformation cannot be found) then a sign test (or a wilcoxon matched pairs test) may be used. A power calculation

can be carried out for the sign test although this too makes some assumptions. This calculation shows that a sample size of N=40 would have >80% power to detect a difference such that the probability of X>0 (where X is the difference in change, as above) is approximately 0.7. This probability is not unrealistic given the data seen previously, and, if the clinically relevant difference detailed above is seen, the probability of X>0 may in fact be increased leading to higher power.

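### At the SAP's two-sided 5% level, the sign-test fallback with N=40 and P(X>0)=0.70 has about 70% power, not the stated >80%

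*Protocol*

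**What the plan says.** Protocol section 13.2 and SAP section 2.3 carry the same argument. If the paired t-test assumptions fail and no transformation helps, "then a sign test (or a wilcoxon matched pairs test) may be used". Power is then calculated for the first of these tests: "A power calculation can be carried out for the sign test (46) although this too makes some assumptions". The result is given as: "This calculation shows that a sample size of N=40 would have >80% power to detect a difference such that the probability of X>0". The value assumed for that probability is about 0.7, with X standing for the paired contrast between two areas.

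Both sections then offer reassurance: "This probability is not unrealistic given the data seen previously, and, if the clinically relevant difference detailed above is seen, the probability of X>0". They go on to suggest that this would push the probability, and so the power, upwards. The difference meant is 3.5 g/m²/h between test cream and no treatment, with a standard deviation of about 8 for the paired difference.

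The protocol treats 40 as the number left after dropout from 50 recruited. SAP section 2.1 plans to recruit 40. The protocol synopsis names 50 participants and says that, if the data do not suit a parametric analysis, "then the sample size would provide greater than 80% power in a non parametric analysis". It names neither the test nor the effect.

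Neither sample-size section gives a significance level. SAP section 7.5 does: "All analyses in this SAP will be carried out with a two sided 5% significance level".

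**The concern.** A power figure can be checked only if its alpha and sidedness are known. The one level the plan commits to is two-sided 5%, and at that level the printed inputs do not give the printed power. The shortfall is 8 to 10 percentage points, too large to be rounding in the power figure itself.

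The fallback is part of the case for the sample size. Protocol section 13.1.4 expects TEWL and redness to be skewed, and SAP section 7.1 keeps the Wilcoxon and sign tests as alternatives if the ANCOVA assumptions are not met. A reader relying on the printed figure would think a switch to the sign test still leaves power above 80%. The sentence about the 3.5 difference adds to that impression.

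**Working it through.** **Inputs.** N=40, P(X>0)=0.70 against a null of 0.50, stated power >80% (Protocol 13.2, SAP 2.3). Two-sided 5% (SAP 7.5). Mean difference 3.5 and SD 8 (Protocol 13.2).

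**Formula.** The usual normal approximation for the sign test is

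power = Φ(2√N·|p − 0.5| − z_α), equivalently N = (z_α + z_β)² / [4(p − 0.5)²].

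**Reproducing the plan's figure.** With N=40 and p=0.70, 2√40 × 0.20 = 2.530.

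- One-sided 5%: Φ(2.530 − 1.645) = Φ(0.885) = 81.2%. N for 80% is (1.645 + 0.842)²/0.16 = 38.6, which fits a stated N of 40.
- Two-sided 5%: Φ(2.530 − 1.960) = Φ(0.570) = 71.6%. N for 80% is (1.960 + 0.842)²/0.16 = 49.1.

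**Checks by other methods, N=40, p=0.70.**

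| Method | One-sided 5% | Two-sided 5% |
|---|---|---|
| Formula above | 81.2% | 71.6% |
| Exact binomial | 80.7% (reject at ≥26; size 4.0%) | 70.3% (reject at ≥27 or ≤13; size 3.8%) |
| Variance under the alternative | 83.3% | 73.3% |
| Same, continuity-corrected | 78.6% | 67.3% |

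No two-sided version reaches 80%.

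**P(X>0) needed for two-sided 80% with N=40.** By the formula, 0.5 + (1.960 + 0.842)/(2√40) = 0.7215. The exact test gives 0.7216.

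**The synopsis number.** With all 50 evaluable, p=0.70 and two-sided 5%, the formula gives 80.7%. The exact test gives 78.2% (reject at ≥33 or ≤17). Exact power moves in steps as N changes (81.0% at N=49), so these values straddle 80%.

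**What a difference of 3.5 implies.** A mean and an SD do not fix P(X>0). With mean 3.5 and SD 8 held constant, and the following shapes assumed for illustration, two-sided 5% power at N=40 is:

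| Assumed shape of the paired difference | P(X>0) | Exact power |
|---|---|---|
| Right-skewed shifted exponential | 0.57 | about 12% |
| Normal, Φ(3.5/8) = Φ(0.4375) | 0.669 | 54.3% (formula 57.1%) |
| Logistic | 0.689 | 64.6% |
| Laplace | 0.731 | 83.5% |
| Scaled t, 3 df | 0.748 | 89.2% |
| Left-skewed mirror of the exponential | 0.76 | about 93% |

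**Wilcoxon for comparison.** In simulation with normal differences, N=40 and two-sided 5%, the Wilcoxon matched pairs test has about 89% power when P(X>0)=0.70 and about 75% at mean 3.5, SD 8.

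**The case against.** Several points on the other side have force.

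- **The input is rounded.** A value of 0.72 would print as approximately 0.7 and give about 80% two-sided. This stands as a possible explanation, but the text prints 0.7. If 0.72 was used, it should say so.
- **The shortfall belongs to the sign test.** The plan also allows the Wilcoxon test, and SAP 7.1 names it first. This stands. It limits the point but does not rescue the figure, because the plan's calculation is expressly for the sign test.
- **The fallback is conditional.** The SAP's primary analysis is an ANCOVA with subject as a random effect, and transformations come into play as well. Skewed raw TEWL does not show that the within-person difference in change will be unfit for a parametric analysis. This stands, and it lowers the weight of the point.

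Three stronger readings are tempting, and the documents do not support them.

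- **That the fallback has only about 55% power at the plan's own effect.** The 54–57% figure assumes normal differences, while the fallback is meant for data on which the parametric assumptions fail.
- **That the sentence about a higher P(X>0) is false.** It is hedged, and some shapes with the same mean and SD do exceed 0.7. It is unsupported rather than refuted.
- **That the synopsis is wrong.** It names 50 participants and neither the sign test nor 0.70, so it is underspecified.

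**Conclusion.** The >80% figure in Protocol 13.2 and SAP 2.3 does not hold as written at the SAP's significance level. At N=40, P(X>0)=0.70 and two-sided 5%, sign-test power is about 70–72%. This takes 0.70 at face value, 40 evaluable participants, and the SAP 7.5 level as the one intended for the power calculation. One-sided 5% matches the printed figure, so a mismatch in sidedness is the likeliest explanation, but the documents do not say how it was obtained.

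The reassurance about a 3.5 difference needs a condition attached: P(X>0) would be 0.67 if differences were normal, and lower or higher for other shapes. The point should be fixed because a stated power is wrong and cheap to correct. It is not critical, because it concerns one fallback test and leaves the ANCOVA, the endpoints and the comparisons as they are.

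**What to change.** In Protocol 13.2 and SAP 2.3:

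- State alpha and sidedness for the sign-test calculation and replace the claim with wording such as: 'two-sided 5% sign test: about 70% power with 40 evaluable participants at P(X>0)=0.70; 80% requires P(X>0) of about 0.72'.
- Say that the figure applies to the sign test and not to the Wilcoxon matched pairs test.
- Qualify the sentence on a higher P(X>0): 'a mean difference of 3.5 with SD 8 does not determine P(X>0); it is 0.67 (54–57% power with 40) if differences are normal and may be lower or higher for other shapes'.

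In the synopsis, state the test, the effect and the evaluable number behind the >80%. For a two-sided sign test at P(X>0)=0.70 with all 50 evaluable, the figure is 78–81%. The 50 in the protocol and the 40 in SAP 2.1 should be reconciled at the same time, so that the evaluable number is clear.

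The cost is wording only. The stated power becomes less favourable. No participants are added and no analysis changes.
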